1. LIST OF ABBREVIATIONS

AE	Adverse Event
ARDS	Acute Respiratory Distress Syndrome
BMI	Body Mass Index
CHMP	Committee for Medicinal Products for Human Use
CI	Confidence Interval
COPD	Chronic Obstructive Pulmonary Disease
CRO	Contract Research Organisation
CUP	Compassionate Use Program
EC	Ethics Committee
ECDC	European Centre for Disease Prevention and Control
eCRF	Electronic Case Report Form
EEA	European Economic Area
EMA	European Medicines Agency
EU	European Union
GCSP	Global Clinical Safety & Pharmacovigilance
GSK	GlaxoSmithKline
HA	Haemagglutinin
HDU	High Dependency Unit
ICU	Intensive Care Unit
ILI	Influenza-like illness
IPCW	Inverse Probability of Censoring Weighting
IPTW	Inverse-probability of treatment weighting
IRB	Institutional Review Boards
IV	Intravenous
NA	Neuraminidase
NAI	Neuraminidase Inhibitor
OM	Otitis Media
OR	Odds Ratio
PSM	Propensity Score Matching
PRAC	Pharmacovigilance Risk Assessment Committee
sPVP	Study-specific Pharmacovigilance Plan
UK	United Kingdom
WHO	World Health Organization

Trademark Information

Trademarks of the GlaxoSmithKline group of companies
DECTOVA

Trademarks not owned by the GlaxoSmithKline group of companies
SAS

2. ABSTRACT

Title

A retrospective observational chart review study to evaluate the clinical effectiveness of treatment with zanamivir 10mg/ml solution for infusion in a cohort of intensive care unit-treated (ICU) patients with complicated influenza infection.

Rationale and background

Despite annual vaccination campaigns, other prevention strategies and available treatments, seasonal influenza accounts for approximately 3-5 million severe infections and 250,000-500,000 deaths worldwide annually. Due to limited treatment options, antiviral drug resistance remains a public health concern. There is an unmet medical need for effective intravenous formulations of antivirals to treat complicated influenza. This proposed study will be implemented at the beginning of the seasonal influenza season following the granting of the marketing authorisation.

Research question and Objective(s)

This study aims to gain an understanding of the clinical management of complicated influenza in ICUs in Europe and to investigate the clinical effectiveness of IV zanamivir in the treatment of patients with complicated influenza in this setting.

Primary objective:

- To compare all-cause in-hospital mortality in a group of ICU-admitted patients with complicated influenza who receive treatment with IV zanamivir as part of their clinical care with all-cause in-hospital mortality in a propensity score-matched group of ICU patients who did not receive this therapy during the same influenza seasons and/or pandemic(s).

Secondary objectives:

- To compare all-cause in-hospital mortality at 7, 10 and 14 days after IV zanamivir treatment initiation/matching in the two groups.
- To understand, through the analysis of historical data, treatment patterns for ICU-admitted influenza patients and factors associated with NAI treatment.
- To estimate, in a time-dependent manner, the crude IV zanamivir treatment effect on all-cause in-hospital mortality in a group of ICU-admitted patients with influenza.

Study Design

The collection of data in this study will be triggered by completion of the first seasonal influenza season following the grant of the marketing authorisation for IV zanamivir in the European Union (EU), the United Kingdom (UK), Norway and Iceland. The collection of historical data from for periods prior to the marketing authorisation for IV zanamivir (henceforth 'historical cohort'), designed to gain an understanding of the clinical management of complicated influenza in European ICUs will run in parallel to a retrospective, observational, comparative chart review. Both will be conducted in patients infected with influenza and admitted to ICU. Patients treated with IV zanamivir will be propensity score-matched to patients who have not received this treatment, with both

patient groups followed up until they experience the event of interest (within-hospital mortality) or are censored.

Population

The study population will consist of ICU patients with severe influenza in various tertiary hospitals in the European Union, UK, Norway and Iceland.

Study Variables to be Captured

- Season/pandemic
- Country/centre
- Influenza strain/sub-type
- Age & Sex
- Body mass index (BMI)
- Smoking status (Current, ex-smoker, never smoked)
- Vaccination status, other antiviral treatments, antibiotics
- Underlying co-morbidities
 - Asthma
 - Chronic obstructive pulmonary disease (COPD)
 - Other pulmonary diseases
 - Other chronic conditions
 - Immunocompromised
 - Pregnancy
 - Obesity
 - Prematurity
- Duration of symptoms prior to hospitalisation/treatment
- Presentation at admission (Influenza-like illness [ILI], pneumonia, otitis media [OM], sepsis etc.)
- Requiring supplemental oxygen
- Mechanical ventilation in ICU
- Days from hospital admission to ICU/critical care admission
- In-hospital corticosteroid administration
- In-hospital antibiotic administration
- Reason why patient has limited treatment options

Data sources

This study will only make use of medical records.

Study size

For the comparative cohort, it has been estimated that a minimum of 450 patients in each exposure arm would be sufficient to detect an odds ratio of 0.5 with 80% power at the 5% significance threshold, assuming a baseline mortality of 12%. Depending on the number of untreated patients in the participating ICUs, the sample size estimation may need to be revisited after the analysis of the historical cohort.

Data analysis

A detailed statistical analysis plan will be written before data collection for the comparative study. Propensity scores will be derived from the predicted probability of IV zanamivir treatment estimated in a multivariable pooled logistic regression model with treatment/no treatment fitted as the binary outcome and the covariates above specified as explanatory variables. Treatment and exposure data will be captured separately for the pre- and post-ICU periods and models will be stratified by season (to control for differences in severity) and by time since illness onset (to facilitate appropriate matching).

The primary analysis will consist of a matched Cox regression model to estimate all-cause in-hospital mortality, presented as a hazard ratio for IV zanamivir treatment vs. matched control. A similar regression analysis will be performed to estimate in-hospital survival on Day 7, 10 and 14 after treatment initiation/matching, and a proportional odds regression model will be fitted to analyse the ordinal scale data on the same days.

Milestones

A study report will be filed with the European Medicines Agency (EMA) within 6 months of the required sample size being achieved. As it is challenging to predict the time required to complete the study, an update report will be filed with the EMA each year, providing details of the number of treated and untreated patients enrolled and guidance on the likely study end date.

3. AMENDMENTS AND UPDATES

Amendment number	Date	Section of the study protocol	Amendment/Update	Reason
01	18-May-20	Sponsor Information Page	The UK sponsor contact address has been updated	Following the change of the sponsor address.
01	18-May-20	7.3.3 Confounders and effect modifiers	Clarification on the co-morbidities has been added as well as additional collection of co-infecting viruses	To take into account the COVID-19 pandemic and any other co-infecting viruses.

4. MILESTONES

Milestone	Planned date
Start of data collection	After grant of the marketing authorisation
End of data collection	After intended study size is reached
Final report of study results	Within 6 months after electronic case report form (eCRF) completion for last subject

5. RATIONALE AND BACKGROUND

5.1. Background

Influenza A is the most common type of circulating seasonal influenza viruses in humans, and can be further sub-typed by its viral surface proteins haemagglutinin (HA) and neuraminidase (NA). Influenza B only circulates in humans but infections occur less commonly. Each year, 5-10% of adults and 20-30% of children will be infected by the influenza virus, with illness generally characterized by fever, myalgia, rhinorrhoea, cough, sore throat and headache. Children aged <2 years, adults over 65 years, pregnant women and people with certain chronic illnesses are at higher risk of serious illness due to influenza, including bronchitis, pneumonia, acute respiratory distress syndrome, myocarditis, encephalitis, and exacerbation of underlying chronic diseases [Fiore, 2011; WHO, 2014]. This in turn leads to a higher risk of hospitalisation. For these reasons, it is advised that high risk groups receive an annual influenza vaccination. Additionally, neuraminidase inhibitors (NAI) are most effective if administered within 48 hours of onset of symptoms in uncomplicated influenza illness and, based on real world observational data, may be effective if administered beyond 48 hours from symptom onset in complicated/severe influenza [Adisasmito, 2010; Louie, 2012; Muthuri, 2013; Muthuri, 2014]. Treatment with NAIs was associated with reduced mortality risk by 19%-87% in complicated influenza patients [Hanshaworakul, 2009; Lee, 2010; Muthuri,

2014], while treatment within 2 days of symptom onset was associated with a reduced mortality risk by 52% compared with later treatment [Muthuri, 2014]. In a meta-analysis pooling data from many studies, treatment was associated with a significant reduction in mortality (Odds Ratio [OR] 0.61, 95% CI 0.41-0.90, I² 5%) in the sub-group of patients in intensive care units (ICU). Similar results have been published for patients hospitalised in ICUs with pandemic influenza. Fifty-eight percent of untreated patients survived versus 75% of patients treated with NAIs [Louie, 2012]. Despite annual vaccination campaigns, other prevention strategies and available treatments, seasonal influenza accounts for approximately 3-5 million severe infections and 250,000-500,000 deaths worldwide each year [WHO, 2014].

Effectiveness of vaccinations and treatments depends on the most common circulating (sub)type of influenza virus in a particular season. Small genetic changes to the influenza virus (antigenic drift) occur constantly and result in a slightly altered influenza virus, against which existing antibodies are still effective. When the genetic composition has drifted sufficiently far away from the original virus for which there is pre-existing immunity, exposure may lead to infection again. Beyond antigenic drift, antigenic *shift* describes an abrupt change in the influenza virus and only occurs in influenza A. It results in a new influenza A virus for which there is no or very little population immunity [CDC, 2014] and can result in a pandemic. The last occurrence was in 2009, when the novel H1N1 virus spread quickly and led to a pandemic influenza outbreak, which affected at least 11,275 cases in the first 23 weeks in the European Economic Area (EEA) alone [ECDC, 2010].

When the H3N2, H1N1 seasonal and 2009 H1N1 pandemic influenza virus demonstrated complete resistance to adamantanes, health agencies recommended using NAIs for treatment of influenza [Fiore, 2011]. The most common NAIs are oral oseltamivir and inhaled zanamivir. However, the H275Y mutation, which is the most common resistance mutation in H1N1 viruses, has been proven resistant against oseltamivir [Takashita, 2015]. The seasonal H1N1 influenza virus that preceded the 2009 pandemic H1N1 strain carried the H275Y resistance mutation and was nearly 100% resistant to oseltamivir [Fiore, 2011], leaving only inhaled zanamivir as an effective treatment option. The occurrence of the H257Y mutation in the H1N1 pandemic in 2009-2010 strain was much less frequent, averaging 1-3%. Therefore, the pandemic influenza virus in 2009 could be treated with both oseltamivir and zanamivir.

In addition to seasonal epidemics and intermittent pandemics, zoonotic strains primarily of avian origin have emerged in recent years and have demonstrated very severe illness in humans, with reported mortality rates of 53% for the H5N1 strain [WHO, 2017] and 41% for H7N9 [Iuliano, 2017]. These strains cause respiratory failure due to lower respiratory tract viral pneumonia progressing to acute respiratory distress syndrome (ARDS), multi-organ dysfunction and cytokine storm. Should these viruses, or future novel reassortment influenza A viruses, acquire the capacity to transmit from human to human, a severe pandemic could ensue. In addition, NAI resistance has been reported for both H5N1 and H7N9, highlighting the need for multiple treatment options in this scenario [De Jong, 2005; Hu, 2013].

Due to limited treatment options, antiviral drug resistance remains a public health concern, and alternative treatments to oseltamivir are needed in case of widespread resistance. Although orally inhaled zanamivir has been shown to be less prone to drug resistance, there is an unmet medical need for patients who are unable to take actively inhaled medications; e.g. children, patients who are not awake or strong enough to inhale, patients with underlying lung disease, or patients on mechanical ventilation. Similarly, some pathogenic strains may require systemic exposure beyond the respiratory tract, and therefore an intravenous formulation may offer benefit beyond that achieved by inhaled zanamivir. Peramivir is the only NAI provided as an intravenous formulation, however it is only approved in the United States, Korea, Japan and Israel as a single infusion for the treatment of acute uncomplicated influenza in patients who have been symptomatic for no more than two days with influenza [Komeda, 2014]. In 2018 peramivir was granted a marketing authorisation the EU. The approved indication is for the treatment of uncomplicated influenza in adults and children from the age of two years. It is not indicated in severe or complicated influenza. Peramivir is also cross-resistant to influenza viruses with the H275Y mutation [Memoli, 2010].

In 2009 GlaxoSmithKline (GSK) initiated the clinical development of an IV formulation of zanamivir (zanamivir 10mg/ml solution for infusion) in response to the influenza A/H1N1 pandemic. A global compassionate use program (CUP) was initiated in May 2009 at the onset of the influenza A/H1N1 pandemic to provide zanamivir aqueous solution on a named-patient basis to seriously ill patients with suspected or confirmed influenza for whom approved anti-influenza drugs were not effective or not feasible. Over 3000 patients worldwide have received treatment within this program and, with some limitations, no safety signals were identified that would impact negatively on the benefit-to-risk balance for zanamivir 10 mg/mL solution for infusion (henceforth referred to as IV zanamivir).

The pivotal Phase III study was the largest randomized controlled trial of antiviral treatment in hospitalised patients with severe influenza illness. It enrolled 626 subjects from 26 countries, including 488 who were confirmed to have influenza and 190 who were in intensive care and/or on mechanical ventilation at baseline. The study did not meet its pre-specified primary endpoint (superiority to oseltamivir or IV zanamivir 300 mg in time to clinical response).

The clinical safety data from the IV zanamivir program are consistent with a hospitalised patient population with serious influenza illness and the known safety profile of zanamivir. No safety signals were identified that would impact negatively on the benefit-to-risk balance for IV zanamivir.

The proposed indication for the product is:

Dectova is indicated for the treatment of complicated and potentially life-threatening influenza A or B virus infection in adult and paediatric patients (aged ≥ 6 months) when:

- *The patient's influenza virus is known or suspected to be resistant to anti-influenza medicinal products other than zanamivir, and/or*

- *Other anti-viral medicinal products for treatment of influenza, including inhaled zanamivir, are not suitable for the individual patient.*

Dectova should be used in accordance with official guidance.

This study is being proposed as a post-authorisation efficacy study to demonstrate clinical effectiveness and a positive benefit-risk assessment in the approved indication.

5.2. Rationale

This proposed study would be ready for implementation following the granting of the marketing authorisation in the European Union (EU), United Kingdom (UK), Norway and Iceland. The study population will be limited to patients in ICU. A study in ICU patients will assess a more homogeneous group of patients who have a higher risk of fatal outcome and who are likely to benefit from an effective IV antiviral formulation and is likely to reflect the target indication.

This observational, retrospective, medical records review study will compare clinical outcomes of complicated influenza patients admitted to ICU who were treated with IV zanamivir as part of their routine medical care with a concurrent cohort of ICU patients who did not receive this therapy. A propensity score matched approach will be used to compare the primary endpoint of all-cause mortality during the influenza hospital stay between treatment groups. A modified ordinal scale of clinical outcomes will be investigated as an exploratory endpoint.

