6. RESEARCH QUESTION AND OBJECTIVE(S)

This study aims to:

- i) gain an understanding of the clinical management of complicated influenza in ICU in Europe, including treatment patterns, monitoring the entry of new anti-influenza treatments and utilisation of diagnostic tests including resistance testing.
- ii) investigate the clinical effectiveness of IV zanamivir treatment in ICU patients with complicated influenza illness. Specifically:

Primary objective:

- To compare all-cause in-hospital mortality in a group of ICU-admitted patients with complicated influenza who receive treatment with IV zanamivir as part of their clinical care with all-cause in-hospital mortality in a propensity score-matched group of ICU patients who did not receive this therapy during the same influenza seasons and/or pandemic(s).

Secondary objectives:

- To understand, through the analysis of historical data, treatment patterns for ICU-admitted influenza patients and factors associated with NAI treatment.
- To estimate, in a time-dependent manner, the crude IV zanamivir treatment effect on all-cause in-hospital mortality in a group of ICU-admitted patients with influenza.
- To compare all-cause in-hospital mortality at 7, 10 and 14 days after IV zanamivir treatment initiation/matching in the two groups.

Exploratory objectives:

- To explore, through inverse-probability of censoring weighting (IPCW) analysis, the effect of non-persistence to exposure status in the analysis of the primary objective, above.
- To define the clinical course of disease for the IV zanamivir and comparator groups, categorized in 6 categories on an ordinal scale as described in Section 7.3.2.
 - The category of each patient on day 7, 10, 14 after IV zanamivir treatment initiation/matching
 - The change in category over time of each patient, from Day 1 to Day 14 after IV zanamivir treatment initiation/matching
- To compare the length of hospitalisation between the two groups
- To compare the length of ICU stay between the two groups
- To summarize associated complications of influenza (bacterial pneumonia, sepsis, myocarditis, encephalitis, acute respiratory distress syndrome, respiratory failure, bronchitis) in both groups.

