7.3.2. Outcome definitions

PART I: Historical Cohort

The aim of the historical cohort is to understand treatment patterns for complicated influenza patients admitted to ICU and factors associated with treatment. Therefore, the outcome will be Neuraminidase Inhibitor treatment versus no Neuraminidase Inhibitor treatment.

PART II: Comparative Cohort

Clinical outcomes – primary endpoint:

- All-cause in-hospital mortality up to end of follow-up (defined in Section 7.7.1).

Clinical outcomes – secondary endpoints:

- All-cause in-hospital mortality up to end of follow-up
- All-cause in-hospital mortality at Day 7, 10 and 14 after hospital admission
- Ordinal scale for clinical course of influenza disease
 1. Discharged from hospital
 2. Not requiring supplemental oxygen
 3. Requiring supplemental oxygen
 4. In ICU, not on mechanical ventilation
 5. In ICU, on mechanical ventilation
 6. Death

Analyses will consider the ordinal scale at Day 7, 10 and 14 after treatment initiation/matching.

Clinical outcomes - exploratory

- All-cause in-hospital mortality up to end of follow-up
- Length of stay in hospital and in critical care unit/ICU
- Summary of associated complications of influenza (bacterial pneumonia, sepsis, myocarditis, encephalitis, acute respiratory distress syndrome, respiratory failure, bronchitis)

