7.6.3. Timings of Assessment during follow-up

The final data collection time for both the historical and comparative cohorts of the study is at hospital discharge, the latest available date before study withdrawal or loss to follow-up, or at day 28 after hospital admission if a patient has not been discharged or has been re-admitted to hospital within the 28-day study period.

The dedicated research nurse(s) at each site will check medical charts of discharged patients to identify eligible patients. [Table 2](#) below outlines for which times each (group of) variable(s) of interest will be collected.

Table 2 Proposed exposure and outcome assessment intervals

Data variable	At hospital admission	Before ICU admission	At/after ICU admission	Hospital discharge OR Day 28 post-treatment
Demographics	X			
Influenza diagnostics/details (e.g. influenza strain/type, diagnostic test)	X			
Other risk factors (confounders/effect modifiers from Section 7.3.3)	X	X	X	
In-patient IV zanamivir treatment	X	X	X	X
Admission to critical care facilities (e.g. ICU/high dependency unit [HDU])	X		X	X
Ordinal scale clinical outcomes	X	X	X	X
Mortality in hospital		X	X	X

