If there are sufficient data, propensity score-matched samples will be created to compare: early (≤ 2 days from symptom onset to treatment initiation) versus late IV zanamivir treatment (> 2 days from symptom onset to treatment initiation); early IV zanamivir treatment versus no treatment; late IV zanamivir treatment versus no treatment. Analyses will also be conducted in the subset of mechanically-ventilated patients, and, if sufficient data are available, an analysis will be conducted on patients infected with influenza viruses where resistance is confirmed. If numbers are sufficient, further stratified analyses will be performed for adults and children (aged < 16 years) as well as for immunocompromised patients.

Following matching, patients will accrue time-at-risk from ICU admission (for IV zanamivir patients who initiated prior to ICU admission), treatment initiation (for IV zanamivir patients who initiated in the ICU) or ICU admission (comparator patients); as the study is conducted among ICU-admitted patients, person-time prior to ICU admission is immortal. Patients will be followed up until they experience the event of interest (death) or they are censored (the earlier of hospital discharge or 28 days post treatment/matching [as applicable]). For the secondary objectives described below censoring will be modified as appropriate (7, 10 or 14 days post treatment/matching).

Primary objective: all-cause in-hospital mortality to end of follow-up

A matched Cox regression analysis will be performed to estimate the association between IV zanamivir treatment and mortality during hospital stay. The treated vs. untreated groups will be compared to obtain the hazard ratio for in-hospital survival. Kaplan-Meier plots will be produced for graphical comparison of survival in the two groups.

Secondary objective: crude all-cause in-hospital mortality to end of follow-up

A crude estimate of the hazard ratio, based on the unmatched sample, will also be obtained using a time-dependent Cox regression model stratified by season, to control for differences in severity.

Secondary objective: All-cause in-hospital mortality at Day 7, 10 and 14

A regression analysis, similar to the primary analysis, will be performed on available mortality data at Day 7, 10 and 14 post treatment/matching.

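### The primary endpoint is labelled in-hospital mortality without a time limit but is defined as 28-day in-hospital mortality, and collection stops at day 28 although the closed chart normally shows how the stay ended

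*Protocol*

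**What the plan says.** **Wording without a time limit.** The Rationale (5.2) says the study will "compare the primary endpoint of all-cause mortality during the influenza hospital stay between treatment groups". The primary objective, in the abstract and in Section 6, is "To compare all-cause in-hospital mortality in a group of ICU-admitted patients with complicated influenza" against a matched group, with no horizon. The primary-analysis paragraph in 7.7.1 proposes a Cox model to "estimate the association between IV zanamivir treatment and mortality during hospital stay", again with none. The secondary mortality objective, by contrast, names days 7, 10 and 14.

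**Defined endpoint.** Section 7.3.2 gives the primary endpoint as "All-cause in-hospital mortality up to end of follow-up (defined in Section 7.7.1"). Section 7.7.1 ends follow-up at death or at censoring, which is "the earlier of hospital discharge or 28 days post treatment/matching".

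**Data collection.** Section 7.6.3 ends collection at discharge, at withdrawal or loss to follow-up, "or at day 28 after hospital admission if a patient has not been discharged". The last column of Table 2, in the same section, counts day 28 from treatment instead. The section also says that the research nurse "will check medical charts of discharged patients to identify eligible patients".

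**Uses of the data.** Section 7.7.2 compares length of hospital and ICU stay by matched t-tests or non-parametric alternatives. Section 7.5 assumes 12% mortality in untreated patients and gives no time horizon for it.

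**The concern.** A reader of the abstract or objectives will take the primary result to cover the whole influenza admission. The analysis covers at most 28 days from treatment or matching. In a prospective study a cap saves follow-up. Here the stay is over before the nurse opens the chart, so the cap saves almost nothing and leaves information unrecorded.

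Three things are at stake. The report could not say what happened to patients who stayed longer than four weeks. Every stay longer than the limit would enter the length-of-stay comparison cut short. And because the collection limit and the analysis limit are counted from different days, some of the 28-day window itself may lack data.

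**Working it through.** **1. Label against definition.** Sections 2, 5.2 and 6 and the primary-analysis paragraph of 7.7.1 carry no day limit. Section 7.3.2 with the follow-up rule in 7.7.1 gives 28 days from treatment or matching. The quantity estimated is therefore 28-day in-hospital mortality.

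**2. What the chart holds.** The charts are those of discharged patients. This must include patients who died, or there would be no primary events to find. A death in hospital on, say, day 35 would normally be in the chart. Under 7.6.3 it is not collected, and under 7.7.1 it falls outside follow-up.

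**3. The two clocks.** Take a patient treated or matched *k* days after hospital admission who is still in hospital. The 7.6.3 text gives 28 − *k* days of data after treatment or matching, against a 28-day window in 7.7.1. For *k* = 5, that is 23 days. Under Table 2 it is 28. A death in the gap lies inside the analysis window but outside the collection window.

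**4. Length of stay.** Under the 7.6.3 text, a patient who stays 40 days has no recorded discharge date. The last recorded day is 28. A t-test or rank test would treat 28 as the length of stay, because neither handles censoring.

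**5. Reproducing the sample size.** Inputs from Section 7.5: untreated risk p₁ = 0.12, odds ratio (OR) 0.5, α = 0.05 (two-sided reproduces the table), 80% power, 1:1, continuity correction.

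- p₂ = 0.5 × 0.12 / (1 − 0.12 + 0.5 × 0.12) = 0.06 / 0.94 = 0.0638
- d = 0.12 − 0.0638 = 0.0562; mean risk p̄ = 0.0919
- n′ = [1.960 √(2p̄(1 − p̄)) + 0.842 √(p₁(1 − p₁) + p₂(1 − p₂))]² / d² = 414.1
- n = (n′/4) [1 + √(1 + 4/(n′d))]² = 449, against 450 stated

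Power at 450 per arm is 80.1%. Expected deaths are 450 × (0.12 + 0.0638) = 82.7.

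**6. Power if the 12% is whole-stay mortality.** Let *f* be the share of in-hospital deaths after day 28. The protocol gives no value, so the range is assumed. Both risks are multiplied by (1 − *f*), and the same formula is solved for power at 450 per arm.

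| *f* | Untreated risk | Treated risk | Deaths counted | Power | Power, OR held at 0.5 |
|---|---|---|---|---|---|
| 0% | 12.0% | 6.4% | 82.7 | 80.1% | 80.1% |
| 5% | 11.4% | 6.1% | 78.6 | 77.7% | 78.0% |
| 10% | 10.8% | 5.7% | 74.5 | 75.0% | 75.7% |
| 20% | 9.6% | 5.1% | 66.2 | 69.0% | 70.5% |
| 25% | 9.0% | 4.8% | 62.0 | 65.7% | 67.5% |

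If the 12% already means mortality within 28 days, the first row applies and nothing is lost.

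**7. Bias.** With equal late shares the odds ratio hardly moves: 0.50 becomes 0.51 at *f* = 30%. It moves only if the shares differ. As an illustration, take equal whole-stay mortality of 12%, with 10% of untreated and 20% of treated deaths falling late. The 28-day risks are 10.8% and 9.6%, a risk ratio of 0.096 / 0.108 = 0.89 and an odds ratio of 0.88. Nothing in the protocol supports those unequal shares.

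**The case against.** The strongest reply is that the 28-day limit is neither hidden nor wrong. Section 7.3.2 ties the endpoint to the end of follow-up, 7.7.1 fixes it, the 7.7.1 heading for the primary objective refers to the end of follow-up, and 7.6.3 speaks of a 28-day study period. A 28-day horizon is a legitimate choice, and later deaths are less specific to influenza. All of that stands. A reader might infer an undisclosed truncation; the cross-reference rules that out.

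A reader might also infer that late deaths are counted as survivors. In the Cox model they are not. Such a patient was alive at day 28 and is administratively censored there, which is valid for the hazard over 28 days. The patient would become a non-death only in the binary mortality analysis that 7.7.1 mentions in passing, or if the result were reported under the unlimited label.

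On power, the 12% is one scenario in a table running from 5% to 25%. Section 7.1 has Part I validate the assumptions, and 7.5 allows the sample size to be revisited, so a lower event rate is partly provided for. That also stands, but those checks need a stated horizon to be checked against.

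Finally, whole-stay mortality has limits of its own: Section 7.9 says deaths after discharge are not captured. This is why it should not simply displace the 28-day analysis. The reply does not answer the mismatch in labels, the two clocks, the truncated stays, or the failure to record an end-of-stay status that the chart normally contains.

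**Conclusion.** The point holds as one of labelling and data collection. The objective and rationale describe a wider quantity than the one defined, and collection stops where the source normally continues. The consequences that follow from the text alone are that no statement about mortality over the whole stay is possible, that stays beyond the limit are truncated in tests that cannot handle censoring, and that the data window may be shorter than the analysis window for patients treated or matched after admission.

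The sizes are conditional. Power falls from 80% to between about 78% and 66% only if the 12% is whole-stay mortality and 5% to 25% of in-hospital deaths come after day 28; the protocol states neither. Distortion of the treatment effect needs late-death shares that differ by arm, for which there is no evidence in the protocol. The documents therefore do not support saying that the primary analysis is invalid, underpowered or biased.

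**What to change.** - Keep the 28-day analysis as primary and call it *28-day in-hospital mortality* in Sections 2, 5.2, 6 and 7.7.1.
- In 7.6.3, remove the day-28 stop for vital status and discharge date. Record both at the end of the influenza hospital stay for every patient. This also repairs the length-of-stay comparison.
- Pre-specify in-hospital mortality to the end of the stay as a supportive analysis.
- Use one day-28 origin in the 7.6.3 text, Table 2 and 7.7.1.
- State in 7.5 the time horizon of the 12% assumption.

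The cost is two eCRF fields from a chart that is already open, one extra analysis and some rewording, all best done before abstraction starts. The drawback is that late deaths are less specific to influenza, which is why the whole-stay analysis is supportive only.
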